**Pre AND Post randomization exclusion criteria:**

16. During study intervention (the first 14 days of the study) subjects shall not receive other types of antibiotics, proton pump inhibitor, or any other drugs which may cause QT interval prolongation. Medications that are not known to cause QT interval prolongation are allowed. Please see **Appendix 1** for a comprehensive list of medications that may cause QT interval prolongation.

Medications included in **Appendix 1** that may be commonly used in young children are:

- a. Pantoprazole (Protonix®): a proton pump inhibitor.
  - b. Famotidine (Pepcid®): anti-H2 medication.
  - c. Macrolide antibiotics (azithromycin, clarithromycin, and erythromycin); quinolone antibiotics (ciprofloxacin, levofloxacin); metronidazole (Flagyl).
  - d. Fluconazole (Diflucan®): anti-fungal.
  - e. Hydroxyzine (Atarax®): anti-H1 medication.
  - f. Diphenhydramine (Benadryl®)
  - g. Ondansetron (Zofran®): anti-emetic.
  - h. Dexmedetomidine (Precedex®): sedative used in the ICU setting.
- If the child is using one of the medications included in **Appendix 1** at the time of enrollment, he/she will not be enrolled in the study.
  - If the child is prescribed with **macrolides**, after enrollment but during the active treatment phase of the study (first 14 days), the study medication use will be discontinued and the child's participation in the study will be terminated.

- If the child is prescribed with one of the medications included in **Appendix 1, with the exception of macrolides**, after enrollment but during the active treatment phase of the study (first 14 days), the study medication use will be discontinued and the child will continue to be followed per study protocol.
- If the child is prescribed with one of the medications included in **Appendix 1** after the active treatment phase of the study (after the first 14 days), no action is required.

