### Other treatments:

General: the child's clinical care will be directed by the participant's treating physician. The investigators will not prescribe any other treatments other than study medications (azithromycin or placebo). These treatments will be recorded and will be included in our analyses (see Analysis Plan Section).

Bronchiolitis clinical care: during the hospitalization, infants will be treated according to a predefined care-path, the SLCH Bronchiolitis Pathway, which is based on the American Academy of Pediatrics guidelines for treatment of bronchiolitis. The SLCH Bronchiolitis Pathway emphasizes supportive care, and strongly discourages use of systemic corticosteroids and antibiotics. All decisions regarding medical treatment during the hospitalization, other than those related to study participation will be made by the child's primary attending physician.

Other treatments (including antibiotics, inhaled corticosteroids, systemic corticosteroids, montelukast and albuterol) may be prescribed by the SLCH physician and/or the child's primary care physician by their clinical judgment, and will be recorded by the study staff in the child's research file. These will be acknowledged in the analysis plan.

Treatment with open-label macrolide antibiotics will not be allowed during the active treatment phase of this study for safety concerns. If macrolide treatment will become mandatory during the active treatment phase of this study, then participation in the study will be terminated for the child and open label macrolide could be prescribed.

Therapy for future wheezing episodes: any therapy for such episodes, such as albuterol, oral/inhaled steroids, montelukast, or antibiotics will be prescribed by the primary care physician per this/her clinical judgment.

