## **F. OUTCOME VARIABLES**

### **1. PRIMARY OUTCOME MEASURES**

- a. Clinical trial outcome: The occurrence of a third episode of post-RSV wheezing measured over a follow up duration of 18-48 months, quantified by a Cox proportional hazards regression model, and compared between the groups.

*Primary outcome assessment:* Episode of wheezing will be detected by the question “Has your child’s chest sounded wheezy or whistling (with and without a cold)? This question was adopted from the International Study of Asthma and Allergies in Childhood (ISAAC) study, and was previously utilized in our pilot APW-RSV study and in the RBEL study. Data collection will be conducted in a standardized way, during study visits and phone calls, utilizing Data Collection Forms that have been modified from our APW-RSV study and in the RBEL study.

*Definition of a new distinct wheezing event vs. continuation of previous wheezing symptoms:* In order to define a new wheezing episode a child should not wheeze for at least 7 days before the new event. If the time frame from the previous wheezing episode (last time that the child wheezed) to the onset of wheezing symptoms is shorter than 7 days, these wheezing symptoms would be attributed to the previous wheezing episode and will not be counted as a new event. This approach was utilized in our previous pilot APW-RSV study.

*Time frame for primary outcome assessment:* For the purpose of this study, wheezing detected during the initial RSV bronchiolitis will not be included in the count of post-RSV wheezing. The time frame for measurement of post-RSV wheezing (and other long-term outcomes) starts at the end of the treatment period (2 weeks after randomization) and ends at end of the follow-up period. Therefore, a wheezing episode that occurs at the first 2 weeks of the study, does not “count” toward the outcome of RW.

- b. Microbiome study outcome: Upper airway microbiome community structure measured at the end of study treatments, and its relationship with the occurrence of post-RSV RW ( $\geq 3$  episodes).

See the analysis plan for details on the analytic approach of the microbiome studies.

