## H. NON STUDY DRUGS

Chronic daily treatment with any medication other than routine vitamins or nutritional supplements, and other than current treatments for the acute RSV bronchiolitis will exclude the child from participation in the study.

Treatment with macrolide antibiotic (erythromycin, clarithromycin or azithromycin) will not be allowed during the active treatment phase of the study due to safety concerns of potential overdosing with macrolides; if this treatment will become mandatory, participation in the study will be terminated.

Other treatments (including antibiotics, inhaled corticosteroids, systemic corticosteroids, montelukast and albuterol) may be prescribed by the SLCH physician and/or the child's primary care physician by their clinical judgment, and will be recorded in the child's research file.

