- a. Demographic: Sex, age, race.
- b. Baseline asthma/allergy phenotypic characteristics: Personal history of eczema, parental history of asthma, peripheral eosinophil count on enrolment.
- c. Environmental phenotypic characteristics: second hand smoking, pet exposure.
- d. Acute bronchiolitis characteristics: Duration of respiratory symptoms before enrolment, and the presence of co-infection with other respiratory viruses during the RSV bronchiolitis (e.g. rhinovirus).

\*The following covariates will be compared between the groups and would be considered to be included in the Cox models:

- a. Age at enrollment (months)
- b. Gender
- c. Race
- d. Birth weight
- e. Length of pregnancy (wks)
- f. Maternal smoking status during pregnancy
- g. Breast feeding status at the time of enrollment

- h. Tobacco smoke exposure (at the time of enrollment and during f/u visits)
- i. Pet exposure (at the time of enrollment and during f/u visits)
- j. History of eczema
- k. Parental history of asthma
- l. Duration of respiratory symptoms prior to randomization
- m. Duration of hospitalization (hours: measured from the time of the Emergency Room visit that triggered the admission and until time of discharge)
- n. Lowest O2 saturation recorded on room air
- o. Antibiotics use during the acute hospitalization. Antibiotic use during the follow up period will be measured as one of the secondary outcomes.
- p. Co-infection with other respiratory virus on enrollment (mainly Rhinovirus)
- q. Complete compliance with study medication (defined as >80% compliance)
- r. Antipyretic (acetaminophen and Ibuprofen) use during the initial RSV bronchiolitis
- s. Day care attendance
- t. Number of siblings in the house
- u. Eosinophil count at enrollment

**Censoring considerations:** All subjects will be censored at the time of the last contact with the subject confirms that they had not experienced the outcome measure. This applies whether the subject is a dropout or has remained on study until the end.

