#### **Sensitivity analyses:**

In the primary outcome analysis, we will implement LASSO using the R package `glm` in models that contain only the fixed covariates. After using LASSO to select a best set of fixed covariates, we will potentially add one or more of the three time dependent covariates to that list using stepwise procedures.

The primary analysis, in subjects who are lost to follow-up, will include only the available data until the time they lost to follow-up. However, we would like to be cautious in interpreting these results because a potential non-random dropout could bias the results. Hence, we will perform sensitivity analyses using multiple imputation.

Additional pre-specified statistical analysis will examine subset differences between children who were intubated during the acute RSV bronchiolitis and children who were not intubated in order to better interpret the results of the primary analysis based on the entire data. This will be performed by the following steps:

1. We will examine potential differences in baseline covariates between children who were and were not intubated. If this analysis will yield at least some suggestion of a between-group difference ( $p < 0.1$ ), the presence/absence of intubation will be included as a covariate in the model that will be used for the primary outcome analysis.
2. We will explore potential interaction between intubation and study treatment assignment although power to detect such differences may be low (no preliminary data is available to project the expected power).

3. We will repeat steps #1 and #2 for examining the effect of any mechanical ventilation (intubation, CPAP, BiPAP).

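### Ending participation for a macrolide in days 1-14 takes the child out before outcomes count, in effect a post-randomisation exclusion from an analysis labelled intent-to-treat

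*Combined protocol and SAP*

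**What the plan says.** Three places end participation because of a macrolide in the first 14 days.

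- **V.C, pre and post randomization exclusion criteria, item 16.** If a macrolide is *prescribed*, "the study medication use will be discontinued and the child's participation in the study will be terminated".
- **V.D, Other treatments.** If a macrolide becomes *mandatory*, "then participation in the study will be terminated for the child and open label macrolide could be prescribed".
- **V.H, Non study drugs.** Macrolides are not allowed "due to safety concerns of potential overdosing with macrolides", and "if this treatment will become mandatory, participation in the study will be terminated".

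For any other Appendix 1 drug in the same two weeks, V.C says "the study medication use will be discontinued and the child will continue to be followed per study protocol". VI.B.2 (Management of SAEs) likewise stops study drug after a related SAE but keeps the child in the study, giving the intention-to-treat approach as the reason.

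On the analysis side, VII.A (General approach) labels the primary analysis intent-to-treat. V.F.1 says the time frame for counting wheezing "starts at the end of the treatment period (2 weeks after randomization) and ends at end of the follow-up period". Under Censoring considerations in VII.A, "All subjects will be censored at the time of the last contact" that confirms no outcome. Under Sensitivity analyses, the primary analysis of subjects lost to follow-up "will include only the available data until the time they lost to follow-up"; multiple imputation is added there as a sensitivity analysis because dropout may be non-random.

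**The concern.** Stopping study drug and stopping outcome collection are separate decisions. The overdosing concern in V.H explains the first for macrolides in particular. Nothing in the documents explains the second, and the plan shows twice that the two can be separated.

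A macrolide order soon after randomisation may reflect the infant's clinical course, so the missing outcomes may be informative. A difference between arms could arise through clinical course. It could also arise through unblinding, because VI.D lets a treating physician learn the assignment in a medical emergency. The direction of any bias is unknown. What is at stake is chiefly whether the intent-to-treat label can stand without qualification.

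**Working it through.** **1. Does the child contribute to the primary analysis?** The window opens at day 14. V.F.1 requires at least 7 wheeze-free days before each new episode, so a third counted episode needs two such gaps. It cannot begin before about day 14 + 7 + 7 = 28. A child last contacted by day 14 is censored before the first possible event and is in no event-time risk set, whether time zero is randomisation or day 14. As a check, children censored before day 14 were added to a simulated set of 188 (placebo/azithromycin 2/2, 8/1 and 20/0). The log hazard ratio (-0.66829883), log partial likelihood (-501.94462614) and log-rank chi-square (11.94645256) were unchanged to 8 decimals.

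The condition is that no later contact confirms outcome status. Adverse events already open are followed to an endpoint under VI.B.2, and such a contact could move the censoring date.

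**2. How many children?** No count is given. Appendix 2 reports 200 recruited and 190 retained, so 200 - 190 = 10 losses from all causes (5%). A child terminated by day 14 misses every later contact and is not retained under Table 2, footnote 3. That Appendix 2 uses the same definition is an assumption. The count due to this rule is probably well below 10: the care pathway strongly discourages antibiotics (V.D), and the study brochure, copied to the primary care physician, says to avoid macrolides (V.E.2).

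**3. Bounds on the planned difference.** Inputs from VII.B.1: four-year rates of 71.6% (placebo) and 55.1% (azithromycin), a difference of 16.5 points. Assume 100 per arm, these rates in the remaining children, and missing outcomes set to the extremes.

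With k missing per arm and f = 1 - k/100:
- lower = f × 16.5 - k (all azithromycin losses are events, all placebo losses event-free)
- upper = f × 16.5 + k (the reverse)

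| Missing | Lower | Upper |
|---|---|---|
| 1 per arm | 0.99 × 16.5 - 1 = 15.3 | 17.3 |
| 2 per arm | 0.98 × 16.5 - 2 = 14.2 | 18.2 |
| 5 per arm | 0.95 × 16.5 - 5 = 10.7 | 20.7 |

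With all 10 in one arm:
- placebo, all event-free: 0.9 × 71.6 - 55.1 = 9.3
- placebo, all events: 0.9 × 71.6 + 10 - 55.1 = 19.3
- azithromycin, all events: 71.6 - (0.9 × 55.1 + 10) = 12.0
- azithromycin, all event-free: 71.6 - 0.9 × 55.1 = 22.0

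The outer range is 9.3 to 22.0 points.

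**4. Hazard-ratio scale, illustrative only.** VII.B.1 gives monthly placebo hazards but not azithromycin ones. The placebo hazards were interpolated and scaled by 1.015 to reach 71.6%. An assumed azithromycin/placebo ratio of 0.49 to month 24 and 1 thereafter gives 55.1%. Assumed follow-up is 57, 66 and 77 children for 44-48, 32-36 and 18-24 months. Imputed events are timed as in the same arm, and event-free children are censored at planned end of follow-up. The expected-count Cox fit gives:
- base: 0.546 (106 events, 95% CI 0.37 to 0.80)
- 1 per arm: 0.534 to 0.564
- 2 per arm: 0.522 to 0.583
- 5 per arm: 0.488 to 0.642 (CI at 0.642: 0.44 to 0.94)
- all 10 in one arm: 0.478 to 0.646

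If the ratio instead tapers over months 18-24, the base is 0.524 and 5 per arm gives 0.469 to 0.618.

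**The case against.** The strongest reply is that the plan already handles this. It censors everyone at last contact, dropouts included, warns that non-random dropout could bias the results, and plans multiple imputation. A terminated child reads naturally as a loss to follow-up, and the doubt about missing-at-random applies to any dropout. Part of this stands: imputation may well cover these children. But the text does not say so, imputation is only a sensitivity analysis, and these losses come from a protocol rule rather than from families who cannot be reached.

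A second reply is that the SAE rule concerns a different event, so there is no contradiction. That is fair. The conflict lies in the reasoning: intention to treat is the stated ground for keeping one child and is not applied to the other.

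Three stronger readings are tempting but unsupported.

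- *The children are removed from the intent-to-treat set.* No section says so; the exclusion is one of effect.
- *They would be hidden from view by arm.* The plan is silent on by-arm reporting, and section VI has withdrawals monitored by the investigators, the institutional review office and the DSMB.
- *Blinding means any imbalance must come through clinical course.* VI.D allows a treating physician to be unblinded.

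**Conclusion.** The point holds as a design choice that should be corrected. A stated rule, not a missing detail, removes certain randomised children from the information used in the primary analysis, while the label says intent-to-treat.

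The likely effect is small. With one or two children per arm the result hardly moves. The wide bounds assign every known loss to this rule and set every outcome to an extreme. They rest on 100 per arm, the planned rates holding in the remaining children, and terminated children counting as not retained. The hazard-ratio figures rest further on azithromycin hazards that the documents do not state. A reader should not infer that the trial's result is materially biased. Losing 10 of 200 (5%) sits inside the 20% dropout allowance of VII.B.1, but that allowance protects power and does nothing about bias.

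Two wording points go with it. The trigger differs: *prescribed* in V.C, *mandatory* in V.D and V.H. And VI.B.2 ends safety reporting with participation yet wants all adverse events to Phone Call-1 at 2 months, leaving new events in a terminated child unaddressed. The latter is unclear rather than contradictory.

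**What to change.** Leave all wording on stopping study drug and on open-label macrolide as it is. Then:

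1. Reconcile the trigger wording in V.C, V.D and V.H. No view is taken here on which is right.
2. Reconcile those sections with VI.B.2 and VII.A. State that stopping study treatment for this reason does not end outcome and safety follow-up unless consent is withdrawn, and that these children are analysed in their randomised arm.
3. For children already terminated, report the number by arm, with the date of and reason for the macrolide.
4. State that they are included in the multiple-imputation analysis of VII.A.
5. Add a two-way bounding analysis: azithromycin children as events and placebo children as event-free, then the reverse. State the times, for example imputed events timed as in the same arm and event-free children censored at their planned end of follow-up.

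Appendix 2 says treatment of the last participant ended in spring 2019, so the text can no longer change any child's first 14 days; it now settles the analysis and the reporting. Wheezing data recovered late, with parental consent, should be supportive only, because long recall differs from calls every two months.

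The cost is a short text change, a line in the participant flow, one extra sensitivity analysis and follow-up of a few families.

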## E. VISIT SPECIFIC PROCEDURES

### 1. OVERVIEW OF STUDY VISITS:

Overall, there are 5 types of scheduled study visits or contacts as follows:

1. Enrollment and Randomization visit (RZ) during the acute hospitalization.
2. Daily follow up during the acute hospitalization (HSP1, HSP2 etc...).
3. At least 2 phone calls during the 2 weeks of active treatment phase of the study (MED 1, MED2). These phone calls will be conducted at least once a week during the 2 weeks in which participants will be treated with the study medications. The goals of these calls are: to monitor medication adherence and potential medications related adverse reactions, to answer families questions regarding study medications, and to schedule the first clinic visit (V1)
4. Clinic visit at the end of study treatment: 14 days following randomization (V1).
5. Follow up telephone calls to obtain clinical outcome (P1-P24): the first phone call will be conducted 6 weeks after the first clinic visit ((V1), 8 weeks from randomization), and then every 2 month. The maximal number of phone calls that a participant may have is 24 calls (if a call has to be done in-lieu of a yearly clinic visit- see next section (page 23, #6) for clarification). This maximal number of calls could be conducted only for participants who is recruited early during the first RSV season (2016-2017) and is followed for the maximal duration of follow-up (48 months).
6. Yearly clinic visits (V2-V5): the first yearly visit will be conducted 6 months after randomization, and then every 12 months. Participants recruited early during the first RSV season (2016-2017) may have up to 4 yearly visits (V2-V5). Participants recruited late during the last RSV season (2018-2019) may have only one yearly visit (V2)- see **Figure 7, and Table 1** for study time-line details.
7. Extended Observation Period by follow up telephone calls. During the extended observation period, we will ask the same questions that have been asked at each follow up telephone call throughout the observational period that started immediately after the initial treatment period. These additional follow up telephone calls will occur approximately every four months starting from the participants final phone call from their initial enrollment observation period. If a participant was enrolled into the study during year one recruitment, we will follow that participant up to four years. If the participant was enrolled during year two recruitment we will follow that participant up to three years and if the participant was enrolled during the final year of recruitment we will follow that participant up to two years. These phone calls will occur until the child reaches the age of seven.

### 2. SPECIFICS OF STUDY PROCEDURES:

Visit	RZ	V1	PC1	PC2	V2 (PC3)	PC4	PC5	PC6	PC7	PC8	V3 (PC9)	PC10	PC11	PC12	PC13	PC14	V4 (PC15)	PC16	PC17	PC18	PC19	PC20	V5 (PC21)	PC22	PC23	PC24
Month	0	0.5	2	4	6	8	10	12	14	16	18	20	22	24	26	28	30	32	34	36	38	40	42	44	46	48
History	√	√	√	√	√	√	√	√	√	√	√	√	√	√	√	√	√	√	√	√	√	√	√	√	√	√
Physical exam a	√	√			√						√						√						√			
Safety / adverse events	√	√	√	√	√	√	√	√	√	√	√	√	√	√	√	√	√	√	√	√	√	√	√	√	√	√
Adherence monitoring	√	√																								
Nasal wash:	√	√			√						√ b						√ c									
• Microbiome	√	√			√																					
• Inflammatory markers	√	√																								
• Viral	√																									
• Antibiotics resistance b	√	√			√																					
• Bio-banking	√	√			√						√ b						√ c									
Nasal brush	√	√			√																					
Blood:	√	√									√ b						√ c									
• CBC & differential	√																									
• Eosinophil count											√ b						√ c									
• Serum IgE		√									√ b						√ c									
• Serum Specific- IgE											√ b						√ c									
• Genetics bio-banking		√																								
• Serum bio-banking	√	√									√ b						√ c									
• Serum Covid-19											√ b						√ c						√			
Stool collection	√	√			√						√ b						√ c									
Urine collection	√	√																								

